## Executive Summary of project

**Background:** Despite advances in efficacious, efficient and safe biomedical tools to reduce HIV transmission and acquisition the HIV epidemic in South Africa (SA) remains an intractable problem, with the lifetime risk of infection approaching 70% for a 15-year-old girl currently living in northern KwaZulu-Natal Province, the Africa Health Research Institute (AHRI) research setting. This is at least in part due to the difficulty in engaging adolescents and youth in HIV interventions. The demonstration of efficacy of interventions in selected populations has not been confirmed when these interventions have been applied at population level.

We aim to integrate novel advances in intervention design, process evaluation and adaptive trials to answer the question, "will innovative and tailored HIV prevention interventions developed in partnership with young people arrest the HIV epidemic as well as improve wellbeing?" We will use the unique opportunity provided by the AHRI longitudinal population cohort of ~20,000, 16-29-year olds located in the epicentre of the HIV epidemic and in whom we are able to longitudinally measure HIV incidence and health outcomes.

We have used participatory methods with realist process evaluation to develop and tailor the interventions to young people's needs. Findings suggested that young people want us to focus on sexual and reproductive health (SRH), including fertility and family planning, sexual and reproductive infections testing and treatment (not HIV necessarily). The also value peer support and health promotion delivered by people of their own age-group and background. We now aim to assess the feasibility, acceptability, and preliminary effectiveness of multiple interventions using a 4-arm factorial trial within a common intervention delivery platform. This approach will motivate rapid selection of interventions to prioritise for further evaluation or scale-up.

The content of the intervention has emerged from formative work conducted between January – June 2019 that demonstrated acceptability and feasibility of :

- 1. Delivering HIV prevention within *Thetha Nami*, an area-based peer-navigator intervention to promote and support psychosocial well-being, youth development, social welfare, and sexual health to young people aged 15-29.
- 2. Adolescent and youth friendly clinics (*Isisekelo Sempilo*) that are linked to existing primary care clinics (PHC). These clinics included fixed buildings situated within urban and peri-urban primary health care clinics, and mobile clinics that visit the peer navigators' areas on a two-weekly basis and are closely aligned with the area PHC clinic. The clinics deliver adolescent-friendly, nurse-led HIV testing, prevention and care integrated with sexual and reproductive health services.
- **3.** Home-based Sexually Transmitted Infection (STI) self-sampling, testing to address the high prevalence of asymptomatic and treatable infections amongst 15-24-year-old men and women living in the study area.

**Study design**: We will conduct a 2x2 factorial design intervention pilot trial including 1500 men and women aged 16-29-years old and living in the AHRI surveillance area. The study duration will be 18 months. For our primary outcomes of interest, we will assess uptake of comprehensive HIV prevention services, including Pre-Exposure Prophylaxis (PrEP) and Universal Test and Treat (UTT) and the reduction of the proportion of individuals at a population level with infectious HIV (population viral load).

**Study Population and Recruitment:** Research assistants will approach n=3000 16-29-year old males and females selected from the demographic surveillance area at their homesteads. We expect that 2000 will still be eligible, i.e. aged 16-29 and still living in the surveillance area. Research assistants will provide information about the study to all eligible participants and consent them to the random offer of HIV or sexual health interventions (Table 1) and follow-up with a survey and HIV testing at 12 months. We anticipate that n=1500 [75% (73-77%)] will consent to participate.

Group	Name	Content
1	SOC	Research assistants refer the consenting participants to Isisekelo Sempilo adolescent and youth friendly services with HIV testing, treatment if positive and PrEP eligibility screening and offer if negative and family planning
2	SRH enhanced Isisekelo Sempilo	Self-collected vaginal and urine samples are collected at enrolment. Research assistants then provide an Isisekelo Sempilo clinic referral appointment for results, treatment, HIV testing, sexual health, fertility, and family planning counselling, including the personal benefits of ART and Undetectable=Uninfectious among those infected, and PrEP for those eligible and who are negative.
3	Peer-support (Thetha-Nami)	The research assistants refer the participant to a Thetha Nami peer- navigator in their community. Peer navigators will assess their health, social and educational needs, provide mentorship, and help them access

 Table 1: Summary of interventions

		the services they need. The peer navigator will facilitate attendance, adherence and retention at the Isisekelo Semnilo clinic
4	SOC + SRH + peer-support	A combination of interventions 2 and 3, to include both self-collected STI testing, nurse led testing and counseling, and referral to a Thetha Nami peer navigator to encourage clinic attendance and sexual health promotion.

**Data. Collection:** Over a period of 12 months after randomisation we will collect routine data on uptake of *Thetha Nami* and Clinical Services as well as adverse events. At 12 months we will approach all those who consented at baseline by phone, in their homes or wherever they prefer to be seen. Following Informed Consent we will conduct a brief redcap survey to collect information on uptake and experience of HIV prevention and care services, uptake of contraception and incidence of pregnancy, mental health (using PHQ9), and quality of life. We will also offer point of care HIV testing and linkage to care, collect dry blood spot for HIV ELISA and HIV viral load, and offer STI testing and treatment to all. In addition, we will conduct a mixed-method process evaluation to collect data on uptake and retention and fidelity of each component of the intervention; assess service users and providers and the community experience, i.e. which facets of the package are valued; and any social harms. Finally, a costing analysis will be undertaken to establish the cost of delivering the intervention through the different models of care.

**Analysis:** With n=1500 we have 90% power to show an increase from 10% linkage to clinical services (current value) in SoC to 22% with the addition of one intervention (peer navigator support only, or SRH only) and 38% in the arm with two interventions (peer support and SRH). We also have the power to detect a reduction of proportion of 16-29-year olds with a detectable HIV viral load from 7% to 3.5% at 12 months.

Our experienced multidisciplinary team of clinical researchers, epidemiologists, social scientists, and biostatisticians will conduct the study over 18 months. By taking a HIV status neutral approach to enrolling participants we will mitigate the effects of stigma on study participation and thus reduce selection bias. By taking a holistic prevention approach - keeping those HIV-ve virus free and identifying those HIV+ve and fast tracking them onto antiretroviral therapy - we will generate high-quality evidence for the effectiveness in reducing population-level risk of acquiring and transmitting HIV. Secondary analysis will look at the effect of the interventions on individual sexual and well-being outcomes. The process evaluation will identify feasibility and fidelity of the intervention components. Ultimately, it will generate evidence on scalable, cost-effective interventions to reduce the impact of HIV on youth in SA.

## Background and work leading to trial:

Why is the study needed now: South Africa (SA) has an estimated 7.2 million people living with HIV – the highest number globally; HIV remains the leading cause of death. HIV incidence has remained stubbornly high, especially in KwaZulu-Natal (KZN) where we have shown an annual incidence of 8% amongst females aged 20-24 and 4% in males aged 25-29. There has been considerable progress in developing efficacious and cost-effective HIV prevention tools. These include HIV point of care tests (POCT) and self-tests; the use of daily oral tenofovir/emtricitabine for Pre-Exposure Prophylaxis (PrEP) which can reduce the risk of acquiring HIV by up to 90%; and HIV treatment with antiretroviral therapy (ART) that reduces mortality and eliminates onward transmission of HIV to sexual partners. However, there remains a disparity between the vulnerability of different subpopulations to HIV and their demand for, access to, and support for optimal use of HIV care and prevention tools. Adolescents are particularly vulnerable. While mathematical models of the study setting predict that reaching those aged <30 with PrEP and universal HIV test and treat (UTT) will be most effective in reducing HIV incidence, multiple trials and demonstration projects of UTT and PrEP have shown that those aged <30 are the hardest to reach and retain. In parallel primary health care systems, particularly in rural setting are failing to reach young people with contraception, resulting in high levels of teenage pregnancy.

Effectiveness of PrEP depends on high uptake and optimal use. There are several challenges to delivering PrEP to young people. First, while PrEP is effective, low levels of adherence resulted in no observed benefit in PrEP trials among women in SA. A meta-analysis of 24,000 PrEP trials found that only 34% of participants aged <30 adhered to PrEP. Second, public health clinics are not effective in linking young men and non-pregnant young women to HIV care. The AHRI population cohort (the study site) despite over 94% knowing where to get ART, we consistently find that <50% of 15-24-year olds have tested for HIV within the previous 12 months, with pregnancy being the strongest predictor of HIV-testing in women. In our UTT trial, where community-based testing improved HIV testing uptake fewer than 25% and 30% of HIV positive men and women aged <25 linked to care.

HIV programmes in rural SA haven't successfully tackled health and social needs of youth: In the AHRI setting over 85% of school-leavers are unemployed; there are high levels of common mental disorders (CMD) which increase with age (rising to 32% of those aged 20-22). Attempting to reduce structural vulnerabilities through multi-level interventions (social asset building and parenting interventions) has been unsuccessful in reaching older adolescents, those out of school, and those with CMD were less likely to access structural interventions. So, young people are disproportionately affected by both facility-level barriers, such as provider attitudes, financial and time costs of visiting a facility, waiting times and stigma of sitting in a clinic waiting room, and delayed service uptake due to competing priorities. In the meantime, fertility and sexual health remain important for young people.

**The burden of Sexual and Reproductive (SRH) morbidity is high in young people:** In a 2016 populationbased study of 15-24-year olds in the study area we found 20% of women and 10% of men had a curable STI with 75% of these reporting no symptoms, and 40% of the women had bacterial vaginosis. Primary health care systems, in rural setting are failing to reach young people with contraception. In the study area teenage pregnancy levels are persistently high, with an annual incidence of teenage pregnancy of 6.4% (5.7-8.6) (unpublished data) and the majority of young women 15-24 only start contraception after their first pregnancy. The barriers to seeking sexual and reproductive health (SRH) services through health facilities (time and cost of travel, waiting times, stigma and attitude of health care providers) mirror the social costs for seeking HIV treatment in young people. We found that home-based self-sampling and treatment for STIs was acceptable and desirable to young people and forms the basis for creating demand for care and prevention of sexually transmitted HIV within community-based SRH services.

**Community-based care can optimise access and support adherence:** Systematic reviews have looked at factors influencing uptake, retention and ART adherence, finding that a) community-based delivery of HIV care (e.g. adherence clubs or community health workers) improve both uptake and retention in low and middle-income settings and are cost effective and b) peers are effective in supporting adherence and virologic suppression including amongst adolescents. However, none of these promising interventions have been tested in young adults for HIV prevention outside of key populations, where there is some evidence that tailored, personalized community-based, peer-led approaches are effective. Since then our formative work has found that community-based delivery of HIV care and prevention with peer support are acceptable and feasible.

In summary we have found that:

- The acceptability and feasibility of *Thetha Nami*, an area-based peer-navigator intervention promoting wider psychosocial well-being and sexual health promotion in addition to HIV prevention to young people aged 15-29: over a four month period 24 pairs of peer navigators approached 5872, 15-29-year-old men and women, of which 5272 (90%) accepted the rapid psychosocial and health needs assessment. Based on this they were identified to need referral or support for health needs n=2419; social welfare needs n=395; educational (skills) support needs 2058; and legal and advocacy support n=294. N=3634 were referred to the *Isisekelo Sempilo* clinics.
- Isisekelo Sempilo clinics which are adolescent and youth friendly clinics that are linked to existing primary care clinics (PHC) and include clinics situated within two accessible and busy urban and peri-urban primary health care clinics and mobile clinics that visit the peer navigators areas on a two weekly basis and are closely aligned with the area PHC clinic. The clinics deliver nurse-led HIV testing, prevention and care integrated with sexual and reproductive health services. To date n= 337 of those referred from the community (~10%) have attended the clinic.
- The acceptability of home-based Sexually Transmitted Infection (STI) self-sampling, testing and the high prevalence of asymptomatic and treatable infections amongst 15-24-year-old men and women living in the study area

# Hypothesis

The evidence suggests that an effective intervention for young people will need to be co-developed with service users and providers to ensure it is acceptable for users and feasible to deliver. Our formative work suggests that 1) The content should focus on fertility and sexual health and 2) the intervention should be community-based and peer-led. We hypothesise that integrating *HIV prevention and care* (including UTT and PrEP) with youth-led services to improve adolescents and young adults *sexual and reproductive health* will improve uptake of HIV prevention and contraception. This will reduce HIV incidence and improve SRH outcomes. The challenges to initiation, adherence and retention of young

people in complex prevention behaviours supports the need to test and refine this hypothesis in a pilot trial prior to full evaluation.

## Study setting:

This study will be embedded in Africa Health Research Institute's (AHRI) HIV prevention programme based in the uMkhanyakude district of KwaZulu-Natal, South Africa. Here where we have established an open cohort of > 20,000 16-29-year olds, in whom we are able to measure exposure to HIV prevention interventions, HIV incidence and health related outcomes. Using the setting as a platform for delivering intervention allows us to offer various combinations of interventions and measure the difference in prevalence of infectious HIV (defined as the population HIV viral load – a HIV status neutral measure which captures the dual aims of a holistic HIV prevention intervention -i.e. staying negative if HIV negative and initiation and retention on ART if HIV positive) associated with intervention delivery as well as response to the different components of the intervention on intermediate outcomes such as uptake and retention in HIV care, PrEP and contraception, and drug levels.

The study area is mostly rural and poor compared with other parts of South Africa, with high levels of unemployment (over 85% of young adults aged 20-24 are unemployed). In the study area 8 out of 100 women aged between 20 and 24 acquire HIV in one year and 4 out of 10 women attending antenatal clinics are found to be infected with HIV. Data between 2011 and 2015 in the study area suggests that sexually active women aged 16-29 and young adult men have an HIV incidence above the threshold of eligibility for PrEP. Within this context, the AHRI has developed the largest population-based HIV incidence cohorts in the world. Moreover, through a Memorandum of Understanding with the Department of Health AHRI has also embedded data collection clerks within the public health clinics to capture electronically any clinical attendance and linking it with the surveillance platform on all consenting attendees. This allows us to measure linkage of individuals to HIV care and use of contraceptive services.

## Study Goals and objectives

### Study aim:

The overarching goal is to arrest the HIV epidemic and reduce its negative impact on young people in SA through *rapidly developing and testing the efficacy and efficiency of tailored HIV care and prevention (including PrEP and UTT) that address demand, optimise access and support adherence in adolescents and young people. Our aim in this phase of the programme is to integrate exciting advances in participatory intervention development, process evaluation and adaptive trials to explore the hypothesis that, innovative and tailored HIV prevention interventions developed with and for young people will optimize models to deliver HIV prevention and care to men and women aged 16-29 living in a high HIV incidence area of rural South Africa. We will use the pilot to optimize the intervention and understand the relative importance of the different components in supporting the uptake of HIV care, prevention and contraception.* 

### Research questions for the pilot trial

1. Will innovative and tailored HIV prevention interventions developed with young people reduce infectious HIV (measured as population HIV viral load) in 16-29-year-old men and women in rural KZN?

- 2. Are youth-led models of care effective in increasing demand for ART based prevention?
- 3. Will delivering HIV care and prevention through sexual and reproductive health services increase demand and improve sexual health?
- 4. What are the costs of delivering this community-based model of integrated care?
- 5. Is it feasible to deliver interventions with high fidelity and acceptability?
- 6. Can we adapt novel methodological approaches to rapidly evaluate the efficacy, sustainability and equity of interventions to reduce infectious HIV?

Specific objectives for the pilot trial:

- 1. Measure the effectiveness of innovative and tailored HIV prevention interventions developed with young people to reduce infectious HIV in 16-29-year-old men and women in rural KZN
- 2. Evaluate the effectiveness and efficiency of sexually transmitted infection tests with sexual health focused HIV prevention counselling to increase uptake of HIV prevention in eligible 16-29-year-olds in rural KZN.
- 3. Evaluate the effectiveness and efficiency of area-based peer-navigator psychosocial support to increase uptake for HIV prevention in 16-29-year-olds in rural KZN
- 4. Assess the acceptability and feasibility of evaluating the effectiveness of multiple combinations of interventions on reducing infectious HIV using multi-arms within a common platform.

### Study Outcome

### Primary outcomes

- 1. Preliminary data on effectiveness of the intervention in reducing infectious HIV measured as the proportion with a detectable HIV viral load (>400 copies per ml) per arm
- 2. The effectiveness of different components of the intervention to improve demand for HIV prevention and treatment: Measured as the proportion who link to clinical services for HIV testing and PrEP/ART counselling within 60 days per arm
- 3. The acceptability and feasibility of recruiting and following up adolescent and youth participants in an HIV prevention trial platform.
  - a. Acceptability of randomizing to an offer of interventions >75% consent to participate in trial
  - Feasibility of collecting the population HIV viral load in > 75% in an intention to treat analysis (i.e. of all trial participants irrespective of engagement in any intervention), 12 months after enrollment.

### Secondary outcomes

- 1. On treatment estimates and comparison of the proportion with an HIV viral load that is undetectable per arm
- 2. HIV treatment outcomes: Proportion with HIV positive test who start treatment per arm; time from randomization to HIV test and treatment initiation per arm
- 3. PrEP outcomes: Proportion of those eligible (based on the South African PrEP eligibility criteria) who initiate PrEP when tested negative; Proportion who remain on PrEP at the end of follow-up; and proportion of new HIV diagnosis per arm.

- 4. SRH outcomes: Proportion start contraception; new pregnancy; and diagnosed with any STI per arm
- 5. The proportion screening positive for mental health outcome per arm
- 6. Proportion retained, defined as attending at least 3 out of 4 follow-up visits (month 1, 3, 6, 9) and receiving appropriate HIV test per arm

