#### Sample size calculation

Based on recent studies at AHRI, we expect that 75% of individuals who are approached will consent to enroll in the study (N=1500), and 80% of those enrolled will be followed up successfully at 12 months (N=1200). We estimate that 10% of those in the SOC arm will access clinical services, and 5-7% (overall) will have a detectable HIV viral load.

With 2000 eligible and assuming that 75% consent to being randomized, we can estimate this proportion (i.e. acceptability of randomisation) with a precision of 1.9%. With 1500 enrolled, assuming that 80% of those enrolled are followed up at 12 months, we can estimate this proportion (i.e. feasibility of collecting outcome data in all enrolled participants) with a precision of 2.0%

With 1500 randomised to one of the 4 arms (375 per arm), assuming that 10% in the SOC only arm access clinical services, we will have 90% power to detect an increase in uptake to 22% with the addition of one intervention (peer navigator support only, or sexual health only). We will also have >90% power to detect an increase in uptake from 22% in the arms with one intervention, to 38% in the arm with two interventions (peer support and sexual health).

With 750 allocated to each delivery model (SOC or peer navigation), assuming no interaction between the sexual health component and the peer navigator support, we will have 80% power to detect a reduction in the proportion of individuals with detectable viral load from 7.0% to 3.4%, or from 5.0% to 2.0%.

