## Eligibility screening and recruitment

**Study Enrolment:** Using procedures that we have used in recruiting for our DREAMS nested cohorts research assistants will approach eligible individuals in their home or a place of their choosing. They will complete a brief eligibility screening questionnaire on RedCap (confirm they are the person randomised, age 16-29, and able to consent). They will be provided with information, i.e. that they have been randomly selected and will be offered a variety of health interventions that they can choose to uptake if they want. HIV testing at baseline is not a condition of participating, however they need to agree to be followed up 12 months following consent to provide a dry blood test for HIV testing and HIV viral load, a POCT HIV test would be offered at the same time. Irrespective of whether or not they consent to the study individuals who test HIV-negative will receive counselling around the benefits of PrEP and HIV-positive individuals will receive counselling around the benefits of immediate starting of ART. Following informed consent, the participant will receive a unique study id and id card. They will be asked to complete a brief enrolment questionnaire, to be completed within REDCAP on a tablet. This will include the date of recruitment, and the id of research assistant who recruited them their area of residence; name, ID (DSID or SA national number), and telephone contact and basic demographics (age, gender). Following which the tablet will reveal the individuals 2X2 randomisation and related participant information sheet. The research assistant will then proceed to explain the intervention/s that the participant is being randomly offered and seek their consent for each component.

- 1. **Standard of Care (SOC):** The participant will be provided with information about and a bar-coded referral slip to a clinical space linked to a primary health clinic (PHC) they can attend either in a busy commercial area with adolescent and youth friendly opening times (e.g. Mtubatuba or KwaMsane) or *nurse-led mobile clinic test* that visits fixed sites across uMkhanyakude on a once per two-week model where they can receive HIV testing and family planning and start ART or PrEP with three monthly follow-up and refills at mobile clinic. If they agree the bar code will be scanned into the tablet.

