**Clinical Follow-up SoC**: Participants who agree will undergo arm specific clinical screening for PrEP eligibility and ART. Screening is based on the South African National guidelines for HIV care and PrEP and includes Point of Care (POC) tests for HIV, creatinine to assess renal function and Hepatitis B, with vaccination offered to those who are negative, pregnancy test for women and sexual behaviour questionnaire to assess eligibility. Patients who are eligible for PrEP will be started in the three clinics that are currently providing PrEP (the mobile vans or the fixed urban adolescent and youth friendly clinic). Everyone will receive contraception; condoms; and HIV negative men are also counselled around the benefits of voluntary medical male circumcision (VMMC) and referred accordingly. A professional nurse will initiate PrEP or ART usually on the same day. The nurses or clinic-based counsellors will provide counselling on adherence and develop an individualized adherence plan.

If the participant agrees to immediate PrEP/ART initiation, s/he will be issued with a month's supply of generic tenofovir disoproxil fumarate and emtricitabine (TDF/FTC) or ART. Baseline and follow-up bloods will be taken and processed as per national guidelines; The professional nurse will register the participant at the clinic (or update the record if the participant is already registered) so that the participant's records are available should the participant seek care there. Participants will receive a phone call seven days after initiating PrEP/ART to complete a standard symptom screen for adverse effects and be referred to clinic for care if necessary. Participants will have a clinic appointment scheduled one month, after PrEP/ART initiation, as per national guidelines; appointments for refills and monitoring will be at two and then three-monthly thereafter. Neutral text message reminders will be provided for participants who have access to private messaging and phone calls. Contact information will be provided for the clinic which participants can contact at any time.

Patients randomised to *Thetha Nami* will be offered their peer navigator support as part of their individualised adherence plan and to support the refills and/or appointment scheduling and reminders. It will be made clear that this referral is conditional to the participant agreeing and can be HIV status neutral.

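### PrEP start is defined only among people found eligible and HIV negative after randomisation, and no listed outcome counts PrEP starters over all randomised

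*Protocol*

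**What the plan says.** Protocol, Secondary outcomes, item 3 gives the PrEP-start outcome as "Proportion of those eligible (based on the South African PrEP eligibility criteria) who initiate PrEP when tested negative". The same item adds "Proportion who remain on PrEP at the end of follow-up", with no denominator stated. Item 2 gives two ART outcomes: "Proportion with HIV positive test who start treatment per arm" and "time from randomization to HIV test and treatment initiation per arm".

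Under Eligibility screening and recruitment, the enrolment paragraph states that "HIV testing at baseline is not a condition of participating". The short enrolment questionnaire records identifiers, contact details, area, age and gender, after which the tablet shows the allocation. PrEP eligibility comes later, at the clinic, from point-of-care tests and a sexual behaviour questionnaire in those who agree. The standard is common to all arms: "Screening is based on the South African National guidelines for HIV care and PrEP".

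Sample size calculation plans attendance by arm: "assuming that 10% in the SOC only arm access clinical services, we will have 90% power to detect an increase in uptake to 22" per cent with one intervention, and then a rise "to 38% in the arm with two interventions (peer support and sexual health").

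Three other places bear on the point. Study design says the trial looks at the effect of each intervention on uptake of PrEP/ART based prevention. Cost, under the study outcomes, asks for the incremental cost per additional person starting and retained, by arm against SoC. Participant Survey and Clinic Linkage analyses linkage by ITT.

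**The concern.** Membership of the PrEP-start denominator requires attending, being tested, being negative and being found eligible. None of this is fixed at allocation, and the first step is what peer support and the sexual health package are designed to change. People who attend only because of an intervention may differ in motivation from those who would attend anyway, so the arms' denominators hold differently selected people.

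An arm that brings in more, but less motivated, attenders could show a lower PrEP-start proportion than SOC while starting more people. The PrEP outcome and the cost per additional starter could then point in opposite directions, in a pilot meant to show which components drive uptake. Even without such selection, a proportion among the eligible says nothing about how many more people reached PrEP. The listed outcomes cannot be combined to recover it: starters per randomised participant equal attendance, times the tested-negative-and-eligible share of attenders, times the conditional start proportion. The middle term is not listed, and linkage is counted within 60 days while PrEP start has no window.

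**Working it through.** **Inputs from the protocol.** 375 per arm; planned attendance 10% (SOC), 22% (either single intervention) and 38% (both). The protocol gives no PrEP start rate and no eligible share, so there is no stated figure for this outcome to reproduce.

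**Attenders.** 375 × 0.10 = 37.5; 375 × 0.22 = 82.5; 375 × 0.38 = 142.5. Figure 2 shows about 40, 85, 85 and 145, which agrees apart from rounding. If the tested-negative-and-eligible share of attenders is the same in every arm, the denominators differ by 142.5 / 37.5 = 3.8 between SOC and the combined arm.

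**Break-even.** With an equal eligible share, an intervention arm starts more people per randomised participant than SOC whenever its conditional proportion exceeds SOC's multiplied by (SOC attendance / arm attendance):

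- one intervention: 0.10 / 0.22 = 0.455
- both: 0.10 / 0.38 = 0.263
- factorial margin (750 v 750): mean attendance (0.10 + 0.22)/2 = 0.16 v (0.22 + 0.38)/2 = 0.30, so 0.16 / 0.30 = 0.533

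Between these values and 1, the arm ranks below SOC on the protocol's measure although it starts more people. The planned attendance figures match the 60-day linkage outcome. If later attendance were 10 points higher in every arm (assumed), the break-evens become 0.20 / 0.32 = 0.625 and 0.20 / 0.48 = 0.417.

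**Illustration (assumed rates).** Half of attenders are eligible and negative, giving 18.75, 41.25 and 71.25. Those who would attend under SOC start at 80%; the extra attenders (22.5 and 52.5 eligible) start at the rate in the first column. The interventions have no effect on starting once a person attends.

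| Start rate, extra attenders | Conditional % (SOC / one / both) | Starters per 375 | % of randomised |
|---|---|---|---|
| 20% | 80 / 47 / 36 | 15 / 19.5 / 25.5 | 4.0 / 5.2 / 6.8 |
| 40% | 80 / 58 / 51 | 15 / 24 / 36 | 4.0 / 6.4 / 9.6 |
| 60% | 80 / 69 / 65 | 15 / 28.5 / 46.5 | 4.0 / 7.6 / 12.4 |
| 80% | 80 / 80 / 80 | 15 / 33 / 57 | 4.0 / 8.8 / 15.2 |

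For example, at 40%: 15 + 22.5 × 0.4 = 24, and 24 / 41.25 = 58%; 15 + 52.5 × 0.4 = 36, and 36 / 71.25 = 51%. An eligible share of 30% or 70% leaves the conditional figures unchanged and multiplies starters by 0.6 or 1.4.

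**Opposite direction.** If usual attenders start at 40% and extra attenders at 80%, starters are 18.75 × 0.4 = 7.5; 7.5 + 22.5 × 0.8 = 25.5; 7.5 + 52.5 × 0.8 = 49.5. The conditional proportions are 40%, 62% and 69%: an apparent effect on starting that is selection alone.

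**ART start over all randomised.** Suppose only the 5-7% with detectable viral load can start, they attend like everyone else, and all who attend start (assumed). Starters per 375 are then 375 × 0.05 × (0.10, 0.22, 0.38) = 1.9, 4.1, 7.1, or with 0.07, 2.6, 5.8, 10.0. Both v SOC differs by 1.40 ± 1.56 points (5%) or 1.96 ± 1.83 points (7%), using unpooled 95% intervals.

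**The case against.** The best reply is that a conditional proportion is an ordinary cascade step, reported per arm with no formal test specified, and that a SAP not seen here may add another denominator. In Sample size calculation, uptake means accessing clinical services, which is a primary outcome analysed by ITT. The cost question needs counts of starters by arm, and the 12-month survey asks all traced participants about service uptake, whether or not they attended. The illustration also uses invented rates, and at these numbers much of it is noise: at 40%, the peer-support margin is 65% of 60 v 53% of 112.5, a difference of 11.7 ± about 15 points; SOC v one intervention is 21.8 ± about 23.5; only SOC v both, 29.5 ± about 21.5, stands clear.

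Much of this stands, and it limits the weight of the point. It does not supply the missing outcome. The protocol itself fixes the denominator. Linkage counts attendance for testing and counselling, not PrEP start. The cost measure is not a listed outcome and is restricted to those retained at 6 months. The survey shows that data are sought, not that such an outcome is defined.

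Four stronger readings are tempting but not supported:

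- **Biased against the interventions.** The direction is unknown, as the opposite-direction case shows.
- **Different eligibility rules by arm.** Screening is called arm specific, but the criteria cited are the same national ones; what differs is who reaches screening.
- **ART start equally exposed.** Time from randomisation to treatment is listed, and ART initiation is named in the ITT linkage measure, so ART has partial cover.
- **Remaining on PrEP wrongly defined.** No denominator is stated, so it is not shown to be wrong.

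**Conclusion.** The point holds for PrEP start. Its denominator forms after randomisation, and no listed outcome gives PrEP start over all randomised, although the design aims at uptake of PrEP/ART based prevention and the cost question counts additional starters. That attender numbers differ up to 3.8-fold follows from the protocol's own planning figures; that the PrEP denominators differ by as much also assumes an equal eligible share. The conditional proportions, starter counts and any reversal rest on assumed start rates and show only what could happen.

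Importance is minor to moderate. These are secondary outcomes of a pilot, linkage read beside the PrEP item partly reveals the problem, and the primary linkage and viral load outcomes are not conditioned in this way.

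**What to change.** In Secondary outcomes, item 3, make the between-arm PrEP-start outcome the proportion of all randomised participants in each arm who initiate PrEP. Keep the proportion among those eligible and tested negative as a descriptive cascade step, read beside linkage. State the denominator for remaining on PrEP.

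In item 2, keep time from randomisation to treatment initiation as the between-arm ART measure and say that it is analysed over all randomised. Treat the proportion of HIV-positive testers who start as descriptive. ART start over all randomised may be tabulated, but on the assumptions above it gives about 2-3, 4-6 and 7-10 starters per 375. The time measure faces the same shortage of events.

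The cost is wording and a few table rows, since linkage and costing already need start data by arm. PrEP start over all randomised is diluted by people who are not eligible, but evenly across arms in expectation. If 40-80% of attenders are eligible and 30-70% of those start in every arm (assumed), power at 375 per arm (two-sided 0.05) is 79% to over 99% for SOC v both, and 30-90% for SOC v one intervention. The single-intervention contrasts should therefore be read as estimates with intervals.
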